Interested patients will be identified through the MS clinic at MGH, the RSVP, the Partners Clinical Trials website or alerted by flyer/letter. Following a phone call to explain the details and requirements of the study, interested participants will undergo a screening survey administered through redcap, link sent by email. This survey will include questions regarding the inclusion/exclusion criteria, the Fatigue Severity Scale (≥ 36), the Beck Depression Inventory (≤ 20), and the Berlin Questionnaire to screen the participant for eligibility. Participants who are eligible and remain willing to participate will then be scheduled for an in-person visit with either the principal investigator (PI) or another physician involved in the study for a baseline visit. The following assessments will be administered by the study PI/research physician at the baseline visit: (1) the Kurtzke Extended Disability Status Scale (EDSS), (2) FSS, (3) Pittsburg Sleep Quality Index (PSQI), (4) Epworth Sleepiness Scale (ESS), (5) Multiple Sclerosis Quality of Life-54 (MSQOL-54). Additionally data will be obtained from patient report and chart review on the patient's history of RRMS or SPMS including time from diagnosis, disease modifying therapy, baseline neurologic symptoms, imaging features such as presence or absence of spinal cord lesions as well as data on medical comorbidities and medications used. Data on the use of caffeine, alcohol and tobacco will also be collected. The participants most recent Vitamin D level will also be obtained from their medical record. This will be collected in order to assess whether response to light therapy differs amongst patients with differing levels of vitamin D deficiency. Studies in patients with MS fatigue show mixed results regarding the relationship of fatigue with vitamin D level and supplementation ¹⁹⁻²¹.

At the baseline visit, participants will be randomized to BWL or DRL. The research coordinator will be aware of the assignment and will distribute the appropriate light therapy boxes during the visit. The PI and research physician will be blinded to treatment assignment so as not to bias follow-up visit assessments. The group assignments will be kept in an excel file that only the research coordinator has access to to maintain blindedness.

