After randomization the subjects will begin the study period. The study period will include a 2-week baseline period without any light therapy treatment, a four week treatment period and a four week follow-up (wash-out) period. Throughout the study period, participants will record their fatigue using the Visual Analogue Fatigue Scale (VAFS) four times daily, starting after waking up, and

every four hours thereafter (at least 3x per day). The VAFS is a simple, validated 10-point scale ranging from 1 to 10 in which participants can report their fatigue as a snapshot at that particular moment.¹⁸ Data collection will occur by participants in self-report fashion on paper that will be returned to the study staff at the end of the study period. During the entirety of the study period including baseline and wash-out, patients will also collect a sleep diary which requires filling out once per day (<1 minute). During the four week treatment period patients will record their use of light therapy in a log as well as any side effects they are experiencing. Patients will be instructed to sit in front of the light box with eyes approximately 18.5 inches from the light source. They will use the box for one hour twice per day, in the morning starting two hours after awakening and in the evening starting 3 hours before bedtime. Eyes should be open while using LT but patients do not have to look directly at the light and can eat, read, watch television etc. during use.

There will be two visits with the principal investigator (PI) including the baseline visit described above, a visit with the PI at the end of the treatment period in which participants will perform a FSS, MSQOL-54 and discuss their experiences with LT. Final follow up surveys (FSS and MSQOL54) will be sent using redcap by email following the 4-week washout period. Patients will be reminded not to reveal their treatment assignment to the examining blinded physician.

- B. Device to be used:** The light box used for LT (SunRay by *The Sunbox Company*, Gaithersburg, Maryland, USA) is approximately 15.5" tall x 23" wide x 3.25" deep and is designed to stand on a desk or tabletop. It can be used both in the home or office. The light is delivered at a downward angle to maximize the effectiveness. The box runs on 124 watts and contains full spectrum 5000k 10,000 lux bulbs. Bright light treatment requires at least 2,500 lux to be effective.¹⁷

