The lights are tested by the supply company before distribution to ensure they meet advertised levels of lux output. Lights are turned on by the study team to make sure they work before being provided to study participants. In cases where bulbs burn out, they are replaced with new bulbs purchased from the same supply company.

VI. BIostatistical Analysis:
Specific data variables, study endpoints, statistical methods, power analysis

The primary outcome measure will be change in the average FSS after

the 4-week study period in the bright light “active” versus the dim light “control” groups. There are no available data on FSS in response to bright LT in pMS. To test the specific aim of change of ≥ 15 points, we used the conventional values of $\alpha=0.05$ and $\beta=0.80$ for 2-tailed tests of probability with equally sized groups. For a difference in ≥ 15 points, with an estimated standard deviation of 15.2 points and mean of 45.9 points from preliminary data collection at the MGH MS Clinic, we require a minimum of 15 people in either group. The primary aim will compare the mean change in FSS scores before initiation and after completion of LT, in an intention to treat analysis comparing the active and control condition groups. The secondary outcome measure will be a change in the global VAFS scores after light therapy in both groups. Frequencies will be used to describe baseline characteristics across treatment arms. χ^2 statistics or Fisher’s exact test will be used to compare the differences between groups. VAFS will be evaluated using a mixed-effects model which accounts for correlation between repeated measurements. Participant logbooks will be used to generate summary statistics and to graphically display fatigue patterns throughout the day among pMS in both groups. Logbooks will also be used to qualitatively assess the safety and tolerability of LT.

RISKS AND DISCOMFORTS:

Device complications/malfunctions and Psychosocial (non-medical risks)

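### The wash-out FSS and all MSQOL-54 data enter no planned comparison; one baseline-adjusted repeated-measures model would use the FSS data and sharpen the primary contrast

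*Combined protocol and SAP*

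**What the plan says.** Section V.A sets out a study period made up of a "2-week baseline period without any light therapy treatment, a four week treatment period and a four week follow-up (wash-out) period". FSS and MSQOL-54 are both among the baseline-visit assessments. Both are repeated at "a visit with the PI at the end of the treatment period in which participants will perform a FSS, MSQOL-54 and discuss their experiences with" light therapy, and both are sent out a third time: "Final follow up surveys (FSS and MSQOL54) will be sent using redcap by email following the 4-week washout period".

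Section VI, whose heading covers variables, endpoints and methods, assigns two outcomes. For the primary, the plan is to "compare the mean change in FSS scores before initiation and after completion of LT, in an intention to treat analysis". For the other: "The secondary outcome measure will be a change in the global VAFS scores after light therapy in both groups". VAFS goes into a mixed-effects model. The rest of the section covers the sample size, baseline descriptions and tests, logbook summaries and graphs, and a qualitative look at safety and tolerability. Section VI mentions neither MSQOL-54 nor the wash-out period.

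**The concern.** Patients complete a third FSS and three MSQOL-54 questionnaires for which the plan has no comparison. FSS is the primary scale, and the wash-out lasts four of the ten weeks. Yet no planned FSS contrast says whether a difference between arms persists once the light stops. No MSQOL-54 score, time point or model is fixed, so any result reported from it could be selected after the data are seen.

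There is also a cost in efficiency. The planned primary analysis compares mean change between two time points. The same FSS data would support a baseline-adjusted model that estimates the same arm difference more precisely and gives a persistence estimate as well.

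**Working it through.** **1. Collection against use.**

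| Measure | Baseline visit | End of treatment | After wash-out | Used in a Section VI comparison |
|---|---|---|---|---|
| FSS | yes | yes | yes | 2 of 3 (not wash-out) |
| MSQOL-54 | yes | yes | yes | 0 of 3 |
| VAFS | daily | daily | daily | mixed model; no wash-out contrast named |

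The wording leaves one ambiguity. Section VI dates the primary outcome to the end of a four-week study period, whereas Section V.A uses that term for all ten weeks, and wash-out also lasts four weeks. The natural reading is the end-of-treatment visit. Under any reading only one later FSS is compared with the starting value, so no end-of-treatment to wash-out comparison is planned.

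**2. The plan's own figure.** Section VI gives 15 per group for a 15-point difference, SD 15.2, two-sided alpha 0.05 and power 0.80 (printed as beta). The normal approximation gives n = 2 × [15.2 × (1.960 + 0.842) / 15]² = 16.1, so 17 per arm. At 15 per arm the power is 0.77 (normal) or 0.74 (t-test). That is close to the stated figure, and this point does not depend on it. I use 15 per arm and SD 15.2 below.

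**3. Assumptions.** The documents give no correlation between visits. I assume equal SDs at all visits and one common correlation r, from 0.6 to 0.8.

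**4. Primary contrast: change score against baseline adjustment.**
- Variance of a change score: 2(1 − r)σ².
- Variance after adjusting for baseline: (1 − r²)σ².
- Ratio: (1 − r²) / [2(1 − r)] = (1 + r)/2.
- r = 0.6 gives 0.80, a 20% reduction. r = 0.8 gives 0.90, a 10% reduction.

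**5. Half-widths of 95% intervals at 15 per arm.** The unadjusted difference at one visit has half-width t(0.975, 28) × 15.2 × √(2/15) = 2.048 × 5.550 = 11.37 points.
- Adjusted wash-out difference: 11.37 × √(1 − r²) = 11.37 × 0.8 = 9.1 (r = 0.6), or 11.37 × 0.6 = 6.8 (r = 0.8).
- Arm difference in change from end of treatment to wash-out: 11.37 × √[2(1 − r)] = 11.37 × 0.894 = 10.2 (r = 0.6), or 11.37 × 0.632 = 7.2 (r = 0.8).

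**6. Patients who miss the end visit but answer the wash-out survey.** Given baseline, the correlation between the two later scores is ρ = (r − r²)/(1 − r²) = r/(1 + r), which is 0.375 to 0.444. If k of 15 per arm miss the end visit and all of them answer later, the effective n at end of treatment is 1 / [(1 − ρ²)/(15 − k) + ρ²/15].

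| k | Without wash-out FSS | With it (r = 0.6 to 0.8) |
|---|---|---|
| 1 | 14 | 14.1 to 14.2 |
| 2 | 13 | 13.2 to 13.4 |
| 3 | 12 | 12.3 to 12.5 |

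The gain is about 0.1 to 0.5 patients per arm.

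**The case against.** The strongest reply is that the omission breaks no promise. Section II aims at FSS reduction after four weeks of light and at feasibility and tolerability; neither quality of life nor persistence is a stated aim. Section VII says only in general terms that the data should inform a larger study of fatigue. A trial of about 30 patients may collect supporting measures, and one sentence calling them exploratory would close much of the gap. Comparing mean change at the target time point is also a legitimate primary analysis. All of this stands, and it limits the weight of the point.

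It does not remove the efficiency argument. The 20% to 10% comes from conditioning on baseline rather than from the wash-out data, so it is a preference for a better method and not the correction of an error. The wash-out FSS adds the persistence estimate and the small recovery in step 6.

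Four stronger readings are tempting, and the documents do not support them:
- **That the wash-out goes unused.** VAFS is recorded through it and enters a planned model, although no wash-out contrast is named.
- **That contrasts will be picked with the data in view.** The text leaves room for this; it does not show it.
- **That persistence can be estimated only to within 11.4 points.** That half-width is for an unadjusted difference and fits neither proposed contrast.
- **That the wash-out survey substantially protects the primary analysis against missed visits.** Putting 0.6 to 0.8 straight into the formula ignores baseline adjustment. It also needs every patient who missed the visit to answer the survey, which nothing in the documents supports. Section III also withdraws patients for certain relapses and therapy changes.

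**Conclusion.** The point holds as a gap in the planned use of data and a missed gain in precision. The wash-out FSS and all MSQOL-54 data have no planned comparison; the validity of the primary test is unaffected.

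The size is moderate: a 20% to 10% lower variance for the primary contrast, and FSS persistence estimates with half-widths of roughly 7 to 10 points. Such intervals are wide, so these results are estimates and not tests. Recovery of information from missed end visits is too small to be a main argument.

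The figures rest on the assumed common correlation of 0.6 to 0.8, equal SDs, complete data in steps 4 and 5, and the clinic SD of 15.2 carrying over to patients selected for FSS of at least 36. The half-widths scale in proportion to that SD.

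**What to change.** In Section VI:

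- Analyse the end-of-treatment and wash-out FSS in one repeated-measures model with arm, time, arm-by-time and baseline-visit FSS, an unstructured within-patient covariance, and a small-sample degrees-of-freedom method such as Kenward-Roger.
- Name the arm difference at the end-of-treatment visit as primary. This also settles the ambiguous wording about the study period.
- Report the wash-out arm difference, and the arm difference in change from end of treatment to wash-out, as secondary estimates with 95% confidence intervals.
- List MSQOL-54 as exploratory, with its summary score and time point fixed in advance.

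The cost is analysis wording only; every measurement is already scheduled. The downside is more results: two for FSS plus those for MSQOL-54. Running MSQOL-54 through all three contrasts (end of treatment, wash-out, change between them) would add three per score, making at least five in all, which is a reason to fix one score and one time point. All of these should be labelled as estimates and not confirmatory tests.

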LIGHT THERAPY FOR THE TREATMENT OF MS-ASSOCIATED FATIGUE

Protocol

NCT03060759

August 8, 2018

Light Therapy for Multiple Sclerosis Fatigue
Detailed Protocol; version 3

I. BACKGROUND AND SIGNIFICANCE:

Historical background, rationale behind the proposed research, and potential benefits to patients and/or society.

Fatigue is the most commonly reported symptom among people living with multiple sclerosis (pMS).¹⁻⁴ More than a quarter of pMS state fatigue is their most disabling symptom.⁵ Despite the impact of fatigue in MS, there are few effective treatment options. Many pMS seek non-pharmacological options for their symptoms but have limited evidence upon which to make important treatment decisions.

Fatigue may have multiple mechanisms in MS including dysfunction of the dopaminergic neurons in the basal ganglia,^{6,7} endocrine dysfunction due to suppression of the hypothalamic pituitary adrenal axis,⁸ cytokine induction in a continuous, pro-inflammatory state of the brain,⁹ and/or reduced function of the frontal cortices.⁶ We hypothesize that supplemental exposure to bright white light will be associated with a reduction in MS-associated fatigue. In a prospective study following pMS, self-reported sunlight exposure was correlated with lower levels of fatigue.¹⁰ Although causality cannot be determined from that study, this suggests a possible therapeutic benefit of light for fatigue in pMS. Light therapy has also been associated with reduction of fatigue in other neurological and medical disorders including Parkinson's disease¹¹, traumatic brain injury¹², seasonal affective disorder¹³ and cancer-related fatigue¹⁴. If mechanisms of fatigue are overlapping across disorders in which bright LT has shown therapeutic benefits, LT may be an unrecognized therapeutic option for fatigue among pMS. The beneficial effects of light on fatigue may be mediated through its direct alerting effects or through its effects as the main synchronizer of the circadian system.

II. SPECIFIC AIMS

Objectives and hypotheses to be tested:

1. To determine whether bright white light (BWL) (active condition) compared to dim red light (DRL) (control condition) will reduce self-reported fatigue among pMS when administered twice daily in one-hour sessions for four consecutive weeks.

Hypothesis 1: Bright white LT will reduce the average self-reported fatigue score on the Fatigue Severity Score (FSS) by ≥ 10 points among pMS with fatigue, compared to pMS treated with dim red LT.

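### Hypothesis 1 specifies a 10-point FSS difference but the sample size is built on 15 points; with 15 per group, power for 10 points is about 41% on the plan's own SD

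*Combined protocol and SAP*

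**What the plan says.** Section II (Specific Aims), Hypothesis 1, states the effect the trial expects: "Bright white LT will reduce the average self-reported fatigue score on the Fatigue Severity Score (FSS) by ≥ 10 points", relative to dim red light.

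Section VI (Biostatistical Analysis) holds the only sample-size justification. It opens with "To test the specific aim of change of ≥ 15 points, we used the conventional values" and repeats the figure: "For a difference in ≥ 15 points". The other inputs are alpha 0.05, a quantity printed as beta = 0.80 (evidently power), a test specified "for 2-tailed tests of probability with equally sized groups", and a spread and level given as "with an estimated standard deviation of 15.2 points and mean of 45.9 points from preliminary data collection". The conclusion is "we require a minimum of 15 people in either group".

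The primary analysis in the same section compares mean change in FSS between the two arms by intention to treat. Section IV gives 1:1 randomization.

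**The concern.** Section VI says it is testing the specific aim, but its figure is not the one in the Specific Aims. Nothing in the protocol presents 10 points as, say, a minimal important difference and 15 as a separate planning value. Both statements are current text. The 15 appears twice and drives the calculation, so it does not look like a single typing slip.

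This matters because required sample size varies with the inverse square of the target difference. Moving from 15 points to 10 multiplies it by (15/10)² = 2.25. A trial sized for the larger difference can easily return a non-significant result when the hypothesised 10-point effect is real. A reader told that the design had conventional power for its aim could then take that result as evidence against a 10-point benefit. Section VII says the data are to inform a larger randomized study, so such a misreading would carry forward.

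**Working it through.** **Inputs.** Target difference: 10 points (Section II) or 15 points (Section VI). SD 15.2, two-sided alpha 0.05, power 0.80 and 15 per group (Section VI). Allocation 1:1 (Section IV). The test is taken to be a two-sample t-test on 28 degrees of freedom, with the normal approximation alongside.

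**1. The plan's own figure (15 points).** The normal-approximation formula is n per group = 2 × (1.960 + 0.842)² × SD² / difference².

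- 2 × (2.802)² × 15.2² / 15² = 16.1, so 17 per group.
- The t-test (noncentral t) gives 17.13, so 18 per group.

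The stated 15 is close to these but slightly low. At 15 per group, power for 15 points is 74% (t) or 77% (normal), not 80%.

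**2. The same formula for Hypothesis 1 (10 points).**

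- 2 × (2.802)² × 15.2² / 10² = 36.3, so 37 per group.
- The t-test gives 37.25, so 38 per group, about 2.5 times the stated minimum (38/15).

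**3. What 15 per group gives for 10 points.**

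- Standardised difference: 10/15.2 = 0.658.
- SE of the difference in means: 15.2 × √(2/15) = 5.55 points.
- Power: 41.3% (noncentral t) or 43.7% (normal).
- Smallest significant observed difference: t(0.975, 28) × SE = 2.048 × 5.55 = 11.4 points. This is also the expected half-width of the 95% CI.
- An observed difference of exactly 10 points: t = 10/5.55 = 1.80, p = 0.082.
- True difference detectable with 80% power: 1.060 × 15.2 = 16.1 points.

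**4. Sensitivity to the SD.** The endpoint is change in FSS, while 15.2 is the SD of scores from preliminary clinic data. The documents give neither an SD of change nor a baseline-to-follow-up correlation r. Assuming equal SDs at both times, the SD of change is 15.2 × √(2(1 − r)), which equals 15.2 at r = 0.5. For 10 points and 15 per group (t-test):

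| Assumed r | SD of change | Power |
|---|---|---|
| 0.3 | 18.0 | 31% |
| 0.5 | 15.2 | 41% |
| 0.6 | 13.6 | 49% |
| 0.7 | 11.8 | 61% |
| 0.8 | 9.6 | 79% |

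Power passes 50% only if the SD of change is below about 13.5, and reaches 80% only at about 9.4.

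**5. Losses.** Section III withdraws participants for certain relapses and for treatment changes, and Section VI makes no allowance for dropout. With 13 analysed per group and SD 15.2, power for 10 points falls to 36%.

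**The case against.** The strongest reply is that 41% rests on an SD that may not fit the endpoint. The figure of 15.2 is not an SD of change. Nor can it be the screening SD of eligible patients: entry requires FSS of at least 36 on a scale ending at 63, and a variable confined to 36–63 has an SD of at most 27/2 = 13.5, or √((45.9 − 36)(63 − 45.9)) = 13.0 if its mean is 45.9. Follow-up scores are not confined in this way, so the SD of change could be smaller or larger than 15.2. If it were below about 13.5, a true 10-point effect would more likely be found than missed.

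This stands as a caveat on the size of the problem. It does not remove the problem: 15.2 is the only SD the plan offers and the one it uses, nothing in the documents supports an SD as low as 9.4, and the 10-versus-15 contradiction holds at any SD.

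Three further points can be made:

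- **The 15-point basis is stated openly.** True, but it is labelled as the specific aim, which it is not.
- **Fifteen is a minimum.** True, but no larger target is stated, and losses work the other way.
- **The trial also studies feasibility and is meant to inform a larger study.** True, but Section VI presents a formal two-tailed test of the primary efficacy aim at conventional power, not a feasibility-based sample size.

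**Conclusion.** The concern holds. Sections II and VI give different target differences for the same aim, nothing reconciles them, and the stated sample size belongs to the one that is not in the hypothesis. On the plan's own inputs, with 15 analysed per group, an observed difference that just meets Hypothesis 1 would not reach significance, and a true effect of that size would be missed more often than detected. Those two statements are conditional on an SD of change of 15.2; over assumed correlations of 0.3 to 0.8, power runs from 31% to 79%, short of 80% throughout. Because this affects the primary hypothesis and the only sample-size justification, it must be corrected.

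**What to change.** Use one target difference in Section II and Section VI. If Hypothesis 1 stays at 10 points and enrolment is unchanged, Section VI could read along these lines:

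> With 15 participants analysed per group, an assumed SD of 15.2 points for change in FSS and a two-sided 5% two-sample t-test, the trial has about 41% power for the 10-point difference in Hypothesis 1, and 80% power only for a difference of about 16 points. The SD of change is not known; power for 10 points would be about 31% if it were 18.0 and about 61% if it were 11.8. The primary result will be read from the estimated between-group difference and its 95% confidence interval (expected half-width about 11 points at SD 15.2). A non-significant result will not be taken to rule out a 10-point benefit.

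In the same edit, correct the printed beta of 0.80 to power of 0.80 (beta 0.20).

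The cost is protocol wording and a less favourable power statement. No participants, visits or procedures are added. Keeping 80% power for 10 points would instead mean 38 per group before dropout at SD 15.2, which is a change of enrolment and not needed to remove the contradiction.

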Participants will be recruited from the MS Clinic at Massachusetts General Hospital (MGH). 700 pMS are followed in this clinic. In preliminary screening, $\sim 2/3$ of MS patients at MGH have a FSS ≥ 36 (mean 45.9, standard deviation 15.2 points) and will be eligible for participation. We will use flyers placed throughout the hospital as well as letters to eligible patients in order to assist with recruitment. We will use MGH's Research Subject Volunteer Program (RSVP), a participant matching service, to identify subjects with enthusiasm for the project. If the participant is a patient of the principal investigator, a research physician or study coordinator will explain the study so they do not feel obligated to participate. Subjects between 18-70 years old will be recruited for they study. For older subjects, best clinical judgment will be used to determine if participation is feasible.

IV. SUBJECT ENROLLMENT:

- A. **Methods of enrollment, procedures for obtaining informed consent, and randomization:** Following a redcap screening survey (Beck Depression Inventory, Fatigue Severity Scale, Berlin Questionnaire, Inclusion/exclusion criteria) and a baseline visit, eligible participants will be consented and randomized using a computer-based randomization generator 1:1 to (a) white LT (10,000 lux), or (b) dim red LT (<300 lux). Dim red LT is a widely accepted controlled condition in clinical studies of LT. In attempt to reduce placebo effect, the participants will be informed that this study will examine the effect of two different light spectra on fatigue and that one will be placebo. They will be informed that they will not know the

group they are in. Informed written consent will be obtained at the time of enrollment at the screening/baseline visit.

V. STUDY PROCEDURES:

A. Study visits and parameters to be measured, data to be collected and when the data is to be collected:

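### On the plan's own inputs, 15 per group gives about 74% power for 15 points (80% needs 18) and about 41% for the 10 points of Hypothesis 1; the SD used is not that of FSS change

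*Combined protocol and SAP*

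**What the plan says.** Section VI (Biostatistical Analysis) holds the only sample-size justification. It sets the target with "To test the specific aim of change of ≥ 15 points", describes the test as "for 2-tailed tests of probability with equally sized groups", and gives alpha as 0.05 and beta as 0.80. The variability is introduced "with an estimated standard deviation of 15.2 points and mean of 45.9 points from preliminary data collection" at the study clinic, and the result is "we require a minimum of 15 people in either group". No formula or test is named and no allowance for dropout is made. The same section says that no data exist on FSS response to bright light in this population.

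Three other statements bear on this:

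- Section II, Hypothesis 1: "Bright white LT will reduce the average self-reported fatigue score on the Fatigue Severity Score (FSS) by ≥ 10 points", relative to dim red light.
- Section VI, primary analysis: "The primary aim will compare the mean change in FSS scores before initiation and after completion of LT", between the two arms by intention to treat.
- Section III.B (Subject Recruitment), on the source of the SD: about two thirds of the clinic's patients "have a FSS ≥ 36 (mean 45.9, standard deviation 15.2 points) and will be eligible for participation".

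**The concern.** There are three separate difficulties, and a labelling slip.

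1. The stated minimum looks too small for its own inputs. The difference is almost exactly one SD (15/15.2 = 0.987), and 80% power at that effect size takes more than 15 per group.
2. The section that sizes the trial calls 15 points the specific aim, while the aim itself says 10. Both are current text about the same primary comparison, and neither mentions the other. A reader of a null result could not tell which effect the trial was designed to detect.
3. The SD belongs to scores at a single time, while the endpoint is a change score. The plan gives neither an SD of change nor a pre/post correlation to convert one into the other.

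The slip is that 0.80 is called beta. Read literally, that would mean 20% power; power of 0.80 (beta 0.20) is evidently meant.

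Anyone interpreting this trial, or planning the larger one it is meant to inform, would rely on a power statement that does not hold as written.

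**Working it through.** **Inputs.** From Section VI: difference 15, SD 15.2, two-sided alpha 0.05, equal groups, power 0.80, stated n of 15 per group. From Section II: alternative difference 10. From Section III.A: eligibility requires FSS of at least 36, on a scale whose maximum is 63.

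**Attempt to reproduce 15 per group.**

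Normal approximation: n = 2 × [(1.960 + 0.842) × 15.2 / 15]² = 16.12, so 17 per group.

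Two-sample t-test (noncentral t, d = 15/15.2 = 0.987): n = 17.13, so 18 per group.

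Other readings at 80% power also fail to return 15:

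- one-sided alpha 0.05: 13 (normal) or 14 (t)
- SD rounded to 15: 16 or 17
- a paired or one-sample t-test: 11

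Lowering power to 75% does give 15 by the normal approximation (16 by t-test).

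**Power at and near the stated size, SD 15.2.**

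| n per group | 15 points, t-test | 15 points, normal | 10 points, t-test | 10 points, normal |
|---|---|---|---|---|
| 15 | 74.2% | 77.1% | 41.3% | 43.7% |
| 16 | 77.1% | 79.7% | 43.7% | 46.1% |
| 17 | 79.7% | 82.0% | 46.0% | 48.3% |
| 18 | 82.0% | 84.1% | 48.3% | 50.6% |
| 38 | 98.9% | 99.0% | 80.8% | 81.8% |

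For 10 points the normal formula gives 2 × [(1.960 + 0.842) × 15.2 / 10]² = 36.27, so 37 per group; the t-test gives 38.

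**What 15 per group does deliver (t-test).** The standardised difference detectable with 80% power is 1.060. At SD 15.2 that is 1.060 × 15.2 = 16.1 points. Equivalently, 80% power requires an SD of at most 15/1.060 = 14.15 for 15 points, or 10/1.060 = 9.4 for 10 points.

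**Which patients does 15.2 describe?** Section III.B can be read two ways. Scores confined to 36–63 with mean 45.9 can have an SD of at most √[(63 − 45.9) × (45.9 − 36)] = √(17.1 × 9.9) = 13.0. So 15.2 cannot be the spread of screening scores in eligible patients with that mean. The more natural reading is that it describes the whole preliminary sample, in which case it is not the spread in the patients to be enrolled. This bound concerns screening scores only and does not limit the SD of change.

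**Sensitivity to the SD of change.** The documents give no correlation, so r below is an assumption. If the SD is 15.2 at both times, the SD of change is 15.2 × √[2(1 − r)]. Power is for 15 per group by t-test.

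| r | SD of change | 15 points | 10 points |
|---|---|---|---|
| 0.3 | 18.0 | 59.7% | 31.3% |
| 0.5 | 15.2 | 74.2% | 41.3% |
| 0.6 | 13.6 | 83.1% | 49.4% |
| 0.8 | 9.6 | 98.5% | 78.5% |

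Under this model the plan's SD equals the SD of change only at r = 0.5. The model ignores the selection of patients with FSS of at least 36, which narrows the baseline spread and so makes these powers too low. As a second illustration, assume bivariate normal scores with mean 45.9 and SD 15.2 before selection, and baseline cut to 36–63. The baseline SD falls to about 7.4, and the SD of change is √[(1 − r)² × 7.4² + 15.2² × (1 − r²)].

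| r | SD of change | 15 points | 10 points |
|---|---|---|---|
| 0.3 | 15.4 | 73% | 40% |
| 0.5 | 13.7 | 83% | 49% |
| 0.8 | 9.2 | 99% | 82% |

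**The case against.** The best defence is that the right SD may be smaller than 15.2. Once selection on baseline FSS is allowed for, a moderate correlation brings 15 per group above 80% for a 15-point difference, and a correlation near 0.8 does so even for 10 points. That stands as a possibility, and it is why 74% and 41% should be read as the consequences of the plan's own inputs and not as the trial's likely power. But the plan does not make that argument and states no correlation. For 10 points it would need an SD of change no larger than 9.4.

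It can also be said that the shortfall at 15 points is modest: under the normal approximation it is two patients per group and 77% against 80%. That is true, and the conflict between 10 and 15 points matters more.

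Finally, the trial is small and exploratory. It has a feasibility aim, says openly that no prior response data exist, calls 15 a minimum, and is meant to inform a larger study. This limits the seriousness of the point. It does not remove it, because the plan still sets out a two-sided hypothesis test with a formal power claim, and the minimum it states is the number in error.

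**Conclusion.** The concern holds. With a difference of 15, SD 15.2, two-sided alpha 0.05 and equal groups, 15 per group gives 74% power by t-test (77% by normal approximation), and 80% needs 18 (or 17) per group. For the effect in Hypothesis 1, power is 41% (44%), and 80% needs 38 (37) per group. These figures rest only on inputs in the documents, on reading 0.80 as power, and on a comparison of two means, since the plan names no test.

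The SD of 15.2 is not an estimate of the SD of the primary endpoint. Actual power could therefore lie on either side of these figures, and the plan does not let a reader tell which. The correlation ranges above are illustrations, not estimates. This should be corrected, but it does not by itself invalidate the design.

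**What to change.** 1. In Section VI, change the label to power = 0.80 (beta = 0.20).
2. If SD 15.2 and 15 per group are kept, replace the sample-size sentence with: *15 per group gives about 74% power for a 15-point difference and about 41% for 10 points (two-sample t-test, two-sided alpha 0.05, SD 15.2), and detects 16.1 points with 80% power; 80% power for 15 points would need 18 per group.*
3. Choose one target effect, with its justification, and use it in both Hypothesis 1 and Section VI.
4. Preferably, rebuild the calculation on the SD of FSS change, or the residual SD after baseline adjustment, in patients with FSS of at least 36. Take the FSS SD in that subset of the preliminary screening data, state the assumed pre/post correlation, and show power over a range.
5. Say whether 15 per group means randomised or evaluable, because Section III.A provides for withdrawals and no allowance is made for them.

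The cost is recalculation and protocol wording, with no added patients; the stated power becomes less favourable. More patients are needed only if the sponsor insists on 80% power at SD 15.2: 18 − 15 = 3 more per group (6 in all) for 15 points, or 38 − 15 = 23 more per group (46 in all) for 10 points.
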